5.2 Registration Procedures

5.2.1 General Guidelines for DF/HCC and DF/PCC Institutions

The 166 patients who participated in the randomized control trial (Aim 1) were all entered into the Clinical Trials Management System (CTMS) OnCore per DF/HCC guidance. As of September 1, 2020, all those who participate in the observational arm (Aim 2) will be also be prospectively registered in OnCore as per DF/HCC Policy REGIST-101.

5.3 Frailty Measures

We will use a combination of validated frailty assessment tools which are listed in Appendix A and summarized below in Tables 1 and 2. Using both the phenotype and cumulative deficit models (see above) is beneficial to provide more validity for a frailty assessment, and cross validity between the two models has been established.^{11,17} At current, there is still some debate as to the true clinical definition of frailty, and different studies have used different approaches to assess the frailty.¹¹ Using both models will allow for a more rigorous evaluation.

Table 1: Summary of cumulative deficit domains

Domain	In-person and Virtual Administration	Variable type	Cut-point
Functional Status in ADLs^{12,18}	Patient questionnaire #1-14 ^{12,19,20}	Binary	See Appendix A
Overall self assessment of health and performance Status^{12,21}	Patient Questionnaire #15-20, verified by physician report	Continuous	See Appendix A
*Weight loss^{3,11,12}	Patient questionnaire #21	Binary	See Appendix A
*Self-reported exhaustion^{3,11,12}	Patient questionnaire #24-25	Continuous	See Appendix A
Psychological Status^{12,18}	Patient questionnaire #26-28	Continuous	See Appendix A

Comorbidity ^{12,18-20}	Medical Record Review	Continuous	See Appendix A
*Physical Function and BMI ^{3,11,12}	Grip strength, gait speed, and BMI recorded by research assistant	continuous	See Appendix A
Cognition ¹⁸	Clock in the Box ²² (in-person) or Clock Draw (virtual) and MoCA ¹⁴ delayed recall administered by research assistant	continuous ¹²	See Appendix A

*Also included in phenotype assessment

Table 2: Summary of phenotype questions

Domain:	Measure:	In-person and Virtual Administration:	Results:
Weight Loss	In last year, weight has decreased by greater than or equal to 10 lbs or 5% of body weight ^{3,11}	Patient questionnaire #21 and medical record review by research assistant	Positive: Patient has lost 10 lbs or more in last year ^{3,11} Negative: Patient has not lost 10 lbs or more in last year ^{3,11}
Self-reported Exhaustion	Two questions from the CES-D Scale ²³ about exhaustion	Patient questionnaire #24-25	Positive: Patient answers: “most of the time” for either question Negative: Patient answers: “some of the time” or “rarely” for both questions ³
Energy Expenditure	Ability to walk ¹¹	Patient questionnaire #4 and ability to complete gait speed test at time of assessment	Positive: Needing assistance with walking or being unable to walk Negative: No assistance needed for walking ¹¹
Gait speed	NIH 4 meter gait speed test ^{24,25}	Administered by research assistant or trained caregiver	Positive: Rapid gait speed less than or equal to cut-points provided by Gill et al. ²⁶ Negative: Rapid gait speed greater than cut-points provided by Gill et al. ²⁶

Grip strength	Jamar Hand Dynamometer (Sammons Preston Roylan, Bolingbrook, IL) grip strength test ²⁶	Administered by research assistant or estimated by the following question: Do you have difficulty gripping with your hands (e.g. opening a jar)? Yes or No.	Positive: Average strength less than or equal to the cut-points provided by Fried et al., ³ or self-reported difficulty gripping Negative: Average strength greater than the cut-points provided by Fried et al., ³ or no self-reported difficulty gripping
----------------------	---	---	--

We will calculate two scores for frailty; one based on the cumulative deficit model and the other on the phenotype model. If patient's score as frail or pre-frail by either method they will be eligible for evaluation by a geriatrician.

For the Cumulative deficit score (table 1), the cumulative total of deficits is determined by adding all of the deficits that are present (deficit present = 1, deficit absent = 0, and for some variables, partial deficit = 0.25, 0.5, or 0.75) and dividing the result by the total number of items in the index. This study will use a frailty index comprising of 43 items (see appendix A). Of note, up to 92 symptoms can be assessed, although as few as 30 items can be used without loss of predictive validity.^{18,20} Furthermore, the actual composition of the index is not crucial. As long as a sufficient number of variables are used, the variables can be selected at random and still yield comparable results.²⁷ After calculating a total frailty score on the 0-1 scale, cut-points of 0-0.2 for "robust", 0.2-0.35 for "pre-frail", and 0.35-1.0 for "frail" will be used to categorize patients, as was done in the Sheppard study.¹⁶

For the Phenotype score (table 2), the 5 phenotype variables will be assessed by obtaining information both from the patient questionnaire and from physical tests administered by the research assistant or patient caregiver. After evaluation, people positive for 3 or more of the factors are categorized as "frail", people with 1 or 2 factors are "pre-frail" and people with no factors are "robust".¹⁰ Of note, all 5 of the phenotype measures are also included in the cumulative deficit assessment.

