5.4 Data Collection Procedures

Patients will be approached or contacted by the research assistant either at their scheduled appointment with the DFCI oncologist (in-person) or shortly after that appointment (virtual). The research assistant will then consent the patients and document consent with either the patient's wet-ink signature (in-person) or the signature of the research assistant verifying that verbal consent was given (virtual). The assessment will be conducted in-person or remotely, by phone or video conference, to preserve the safety of our patient population during the ongoing COVID-19 pandemic.

In-person assessments will begin with a 28-item self-report questionnaire (see appendix B) filled out by the patient. Next, the research assistant will administer the delayed recall section of the Montreal Cognitive Assessment (MoCA), clock-in-the-box test, grip strength test, and gait speed test. That will end the in-person frailty assessment. Virtual assessments contain minor changes to accommodate remote completion. The 28-item questionnaire, MoCA recall, and modified Clock Draw are conducted by the research assistant during a telehealth appointment. A patient caregiver will be trained to administer a remote gait speed test with a 4-meter strip of

ribbon that will be mailed in advance. Grip strength will be estimated using the following question: *“Do you have difficulty gripping with your hands (e.g. opening a jar)? Yes or No.”*

At baseline, the research assistant will perform a medical record review to obtain comorbidity information and body mass index. A follow up medical record review will be completed at one year from enrollment in order to obtain the outcome data listed in Table 3, which are all secondary outcomes of interest. There will also be general periodic assessments for overall survival.

Table 3: Summary of outcomes

Outcome:	Timeline for assessment:	Operationalization	Obtained from:
Survival*	6 months, 1 year	Overall survival	Patient medical record and outside records
Disease severity	Baseline	Disease Severity	Patient medical record and outside records
Treatment assignment	6 months	Supportive care only vs. chemotherapy vs. low dose chemotherapy vs. investigational treatment; any disease-modifying treatment versus not	Patient medical record and outside records
Hospitalizations	6 months	Number and length of hospitalizations since enrollment	Patient medical record and outside records

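### Section 5.3 divides the cumulative-deficit score by a fixed 43 items and gives no rule for unassessed items; applied literally, this can only lower the score

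*Combined protocol and SAP*

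**What the plan says.** Section 5.3 gives one formula for the cumulative-deficit score. For the numerator, "the cumulative total of deficits is determined by adding all of the deficits that are present"; the score then comes from "dividing the result by the total number of items in the index". The same paragraph fixes the length: "This study will use a frailty index comprising of 43 items". The item codes are "deficit present = 1, deficit absent = 0, and for some variables, partial deficit = 0.25, 0.5, or 0.75", so there is no code for an item that was not assessed. The score is cut at 0.20 (robust to pre-frail) and 0.35 (pre-frail to frail). The paragraph also remarks that "as few as 30 items can be used without loss of predictive validity".

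The protocol does expect some physical measures to be unavailable. The footnotes to the item list in Appendix A let items 22 (difficulty gripping) and 23 (self-reported walking pace) stand in for the physical test, but only in the phenotype score. For remote assessments, section 5.4 says: "A patient caregiver will be trained to administer a remote gait speed test", using a ribbon sent by post.

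No section gives a reduced denominator, a minimum number of items or an imputation rule for the cumulative-deficit score.

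**The concern.** A fixed denominator is harmless when all 43 items are recorded. When some are not, the literal formula adds nothing to the numerator for them and still counts them in the denominator, just as if the deficit had been looked for and found absent. The error then runs one way, towards a less frail category.

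The two walk-speed items (38 and 39) are the clearest candidates. They need a test that some patients cannot do and that, in remote assessments, depends on a caregiver. If missing items are related to frailty or to assessment mode, the misclassification is not random. Section 4.0 dates both virtual assessment and the lowering of the age limit from 75 to 70 to about September 2020, so an error related to mode would also be mixed with age and calendar time.

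Frailty category is the Aim 1 exposure (sections 3.1 and 6.1), with 1,620 patients hoped for (section 6.3).

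**Working it through.** **Inputs.** Formula, index length and cut-points: section 5.3. Item list: Appendix A. Number of unassessed items per patient, m: not in the documents, so shown as an assumed range.

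**1. The plan's own figure.** Questionnaire items 1–28, medical record items 29–36 and staff-assessed items 37–43 give 28 + 8 + 7 = 43. The stated length reproduces.

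**2. Cut-points as deficit sums.** 0.20 × 43 = 8.60 and 0.35 × 43 = 15.05.

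**3. Effect of m unassessed items.** Let D be the sum of observed deficits. The literal score is D/43 and the score on assessed items is D/(43 − m). Their ratio is (43 − m)/43, which never exceeds 1. The proportion needed on the assessed items to reach a category is therefore 8.60/(43 − m) or 15.05/(43 − m).

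| m | Items assessed | Multiplier | Effective 0.20 cut | Effective 0.35 cut | Sums scored robust on 43 but pre-frail on assessed items |
|---|---|---|---|---|---|
| 1 | 42 | 0.977 | 0.205 | 0.358 | 8.5 |
| 2 | 41 | 0.953 | 0.210 | 0.367 | 8.25–8.5 |
| 5 | 38 | 0.884 | 0.226 | 0.396 | 7.75–8.5 |
| 7 | 36 | 0.837 | 0.239 | 0.418 | 7.25–8.5 |
| 13 | 30 | 0.698 | 0.287 | 0.502 | 6.0–8.5 |

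Sums move in steps of 0.25. A score of exactly 0.20 is taken as pre-frail, because the stated ranges share that value; this matters only for D = 6.0 at m = 13. The row m = 2 is both walk-speed items, and m = 7 is every staff-assessed item.

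**4. Examples.**
- m = 2, D = 8.5: 8.5/43 = 0.198 (robust) against 8.5/41 = 0.207 (pre-frail).
- m = 2, D = 15: 15/43 = 0.349 (pre-frail) against 15/41 = 0.366 (frail).
- m = 5, D = 8.5: 0.198 (robust) against 8.5/38 = 0.224 (pre-frail).
- m = 5, D = 14: 14/43 = 0.326 (pre-frail) against 14/38 = 0.368 (frail).

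**5. Can a frail patient be scored robust?** A score of at least 0.35 on the assessed items must fall below 0.20, so (43 − m)/43 must be below 0.20/0.35 = 0.571. That needs m of at least 19. At m = 13, 0.35 becomes 0.35 × 30/43 = 0.244, still pre-frail. Within the range shown, the shift is one step.

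**6. Not done versus unable.** If both walk tests were missed through inability and scored as deficits, the score would be (D + 2)/43. With D = 8.5 that is 10.5/43 = 0.244, against 0.207 on recorded items only and 0.198 literally. The reason for a missing test can therefore matter more than the denominator.

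**The case against.** The strongest reply is that section 5.3 simply gives the complete-data formula. A reader might infer that the study divides by 43 even for incomplete assessments and counts missing items as zero. The documents do not say so; they are silent, and the scoring program may already handle missing items sensibly. This stands: what can be shown is a missing rule and the direction of the literal formula, not an error in operation.

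Several limits on the harm also stand:

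- **Few items are obvious candidates.** BMI comes from the medical record (section 5.4). Poor recall and poor clock drawing already score as deficits, and the clock test has a virtual version. Remote gait is meant to be tested, not skipped.
- **Other items partly compensate.** Help with walking (item 4), self-reported pace (item 23) and needing help to complete the assessment (item 43) all add deficits. Each is worth at most 1/43 = 0.023.
- **The phenotype score catches many patients.** One positive factor makes a patient pre-frail, and Table 2 lists ability to complete the gait test under energy expenditure, although Appendix A lists item 4 alone there. Being frail or pre-frail on either score is enough for geriatrician evaluation. The protection is partial, because the phenotype contains no cognitive item and does not restore the 0.35 cut on this index.
- **The main contrast ignores the 0.35 cut.** Section 6.1 combines frail and pre-frail for Aim 1, so shifts between them affect only the three-group comparison, planned if power allows.

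The 30-item remark might be read as already supporting a denominator of assessed items. It concerns how long an index needs to be and is not a missing-data rule.

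**Conclusion.** The point holds as a gap in the scoring rule with a known direction. Taken literally, section 5.3 lowers the score of any incompletely assessed patient with at least one observed deficit, by the factor (43 − m)/43. With m = 2, the only patients moved at the lower boundary are those with deficit sums of 8.25 or 8.5; with m = 5, those from 7.75 to 8.5. What is at risk is the Aim 1 grouping, mainly at the robust/pre-frail boundary and in the three-group comparison.

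Two stronger conclusions are not supported. Frail patients scored as robust would need at least 19 unassessed items. Biased Aim 2 entry through remote assessment does not fit the dates: section 8.0 schedules the end of Aim 2 enrolment for May 2018, section 5.1 confirms closure, and virtual assessment came around September 2020. Aim 2 eligibility was also partly protected by the either-method rule.

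The direction of misclassification is clear under the literal reading, but its effect on the survival contrast is not. Moving borderline patients down changes the case mix of both groups. The size depends on the missing-item rate, which the documents do not give, and on how the two frailty scores are combined for Aim 1, which section 3.1 does not spell out. It may be small. The change is still worth making because it costs little.

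**What to change.** In section 5.3, define the index as the sum of deficits divided by the number of items with a recorded value, calculated only when a pre-set minimum is recorded and otherwise set to missing. Thirty of 43 is a reasonable minimum, but it is a choice to be stated as such. Score a test not done because of physical or cognitive inability as a deficit, and treat a test not done for logistical reasons as missing. Record the reason from now on.

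Check what the scoring program does at present. If it divides by 43 regardless, re-score the stored Aim 1 assessments before the Aim 1 analysis. Report the number of missing items by assessment mode, so that readers can judge the size of the effect.

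The cost is a few sentences and, if needed, one re-run of the scoring. A few patients below the minimum lose a score. For past assessments the reason a test was not done may not be recoverable; in that case, show the results both ways.

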5.4 Data Collection Procedures

Patients will be approached or contacted by the research assistant either at their scheduled appointment with the DFCI oncologist (in-person) or shortly after that appointment (virtual). The research assistant will then consent the patients and document consent with either the patient's wet-ink signature (in-person) or the signature of the research assistant verifying that verbal consent was given (virtual). The assessment will be conducted in-person or remotely, by phone or video conference, to preserve the safety of our patient population during the ongoing COVID-19 pandemic.

In-person assessments will begin with a 28-item self-report questionnaire (see appendix B) filled out by the patient. Next, the research assistant will administer the delayed recall section of the Montreal Cognitive Assessment (MoCA), clock-in-the-box test, grip strength test, and gait speed test. That will end the in-person frailty assessment. Virtual assessments contain minor changes to accommodate remote completion. The 28-item questionnaire, MoCA recall, and modified Clock Draw are conducted by the research assistant during a telehealth appointment. A patient caregiver will be trained to administer a remote gait speed test with a 4-meter strip of

ribbon that will be mailed in advance. Grip strength will be estimated using the following question: *“Do you have difficulty gripping with your hands (e.g. opening a jar)? Yes or No.”*

At baseline, the research assistant will perform a medical record review to obtain comorbidity information and body mass index. A follow up medical record review will be completed at one year from enrollment in order to obtain the outcome data listed in Table 3, which are all secondary outcomes of interest. There will also be general periodic assessments for overall survival.

Table 3: Summary of outcomes

Outcome:	Timeline for assessment:	Operationalization	Obtained from:
Survival*	6 months, 1 year	Overall survival	Patient medical record and outside records
Disease severity	Baseline	Disease Severity	Patient medical record and outside records
Treatment assignment	6 months	Supportive care only vs. chemotherapy vs. low dose chemotherapy vs. investigational treatment; any disease-modifying treatment versus not	Patient medical record and outside records
Hospitalizations	6 months	Number and length of hospitalizations since enrollment	Patient medical record and outside records
Emergency department visits	6 months	Number of ED visits	Patient medical record and outside records
Code status documentation	6 months	Code status entered into the medical record	Patient medical record
Continuation of care at DFCI	6 months	Number of visits and length of follow-up at DFCI; receipt of treatment at DFCI	Patient medical record
Δ Number of medications	Baseline to 3 months	Overall number of medications = number of cancer meds + number of non cancer meds	Patient medical record
Δ Blood pressure	Baseline, 6 months	Measured at each visit	Patient medical record
Content Analysis of Notes	6 months	Only patients randomized to geriatrician	Patient medical record

*primary outcome

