Frailty is a dynamic process that can worsen or improve over time. For example, elderly cancer patients who undergo inpatient geriatric assessment and management have been shown to become less frail, more likely to return home, and less likely to have cognitive or functional decline.⁷ Inpatient geriatric co-management has also been shown to substantially improve mood, social function and pain management post-discharge.⁸ A systematic review of geriatric evaluation and management of older adults with blood cancers found that non-oncologic interventions are implemented by geriatricians in over 70% of patients, most often targeting nutrition, mood, physical function, polypharmacy, and social function.⁴

While there are limited studies regarding geriatric co-management in the outpatient hematology setting, and no randomized controlled trials to determine the best model of

delivering such care, observational research is instructive. Elderly AML is an excellent example: our own work has shown that markers of frailty are independent prognostic factors for death in models that included cytogenetic risk group, even for those patients with good baseline performance status (ECOG 0-1).⁹ Given this context, we are interested in measuring the frailty of older adults with blood cancers with precision, determining how much it contributes to prognosis compared with clinical disease-specific measures and molecular markers, and determining if co-management by a geriatrician embedded in the oncology clinic can decrease frailty and improve disease-related outcomes.

Indeed, we have begun to see the increased burden of caring for elderly patients in hematologic oncology at Dana-Farber. During the period March 2013 to February 2014, for patients 75 and older, we had 3429 clinical visits in lymphoma (674 unique patients), 1704 for leukemia/related disorders (318 unique patients), and 3,245 for multiple myeloma (516 unique patients). Our older patient volume reflects an outstanding opportunity to both improve our care delivery and research the impact of frailty on disease outcomes. We wish to launch a research program to engage these patients in formal geriatric assessment and management, with the aim of addressing this important clinical and data gap.

2.2 *Frailty Assessment*

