3.0 OBJECTIVES/STUDY AIMS

The goal of this study is to establish a research program – the Older Adult Hematologic Malignancy (OHM) program – that will address important gaps in data about how best to care for older adults with hematologic malignancies. It is clear that markers of frailty are important predictors of tolerance of therapy and survival, but few studies have assessed their value in this population. Geriatric assessment and co-management are associated with improvements in quality of life, resource utilization and survival, but have not been tested scientifically in hematologic malignancies. We therefore propose the following specific aims:

3.1 Specific Aim 1

Characterize the prognostic value of frailty as compared to clinical prognostic models for older patients with blood cancers. We will perform a combined frailty

assessment in patients 70 and older who present to DFCI with a new diagnosis of MDS or a hematologic malignancy. Patients will be categorized as robust, pre-frail or frail based on their frailty score. We will then determine how the presence or absence of frailty predicts important outcomes such as treatment, resource utilization and mortality. In a subset of patient who specifically agree, frailty will be re-assessed at subsequent visits.

Hypothesis: Frailty will predict survival for those older patients with low-risk disease on molecular markers/disease-based risk systems, but be trumped by these for patients with high-risk disease.

3.2 Specific Aim 2

Determine if co-management of frail and pre-frail older adults with blood cancers by an embedded geriatrician improves outcomes. Patients who score as pre-frail or frail will be randomized to geriatric assessment and co-management with a geriatrician or usual care. They will be followed for disease-specific outcomes, with the primary outcome being overall survival at 1 year.

[figure not shown]
Hypothesis: For those assessed to be frail with rigorous measurement, co-management by an embedded geriatrician will improve overall survival at one year.

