4.0 ELIGIBILITY

All patients aged 70 and older who present for an initial consultation at the DFCI for MDS or a hematologic malignancy (transplantation consultation excluded) are eligible. Note that until September 2020, before virtual assessments, only patients aged 75 and older were eligible due to resource limitations; this has been changed to include patients aged 70 and older because we can now accommodate more patient assessments virtually. For Specific Aim 2, insurance information will be reviewed to ensure geriatric referral is covered for all potential participants. This step will allow us to avoid a situation arising wherein a participant is randomized to geriatric co-management, yet their insurance does not cover geriatrician visits. As baseline geriatric assessment by our research assistant and later randomization to co-management by a geriatrician are currently precious resources, in practicality, to be eligible, patients will have to present on one of the three days per week that geriatric assessments are available, and be willing to be seen for geriatric co-management on one of the two geriatrician clinic days.

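### The 3-month medication outcome is analysed only as cancer plus non-cancer drugs, so its result cannot be read as an effect, or lack of effect, on non-cancer drugs

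*Combined protocol and SAP*

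**What the plan says.** Table 3 (section 5.4) lists the change in number of medications over the window "Baseline to 3 months", measured as "Overall number of medications = number of cancer meds + number of non cancer meds". The text introducing the table describes its contents as outcomes "which are all secondary outcomes of interest", with survival alone marked as primary.

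Section 4.0 admits patients who "present for an initial consultation at the DFCI for MDS or a hematologic malignancy". Section 3.1 describes the Aim 1 population as having a "new diagnosis of MDS or a hematologic malignancy".

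Section 6.2 models the effect of co-management on the Table 3 outcomes, adjusting for age, gender, race-ethnicity and disease type. One of those outcomes is treatment assignment at 6 months, which includes "any disease-modifying treatment versus not". Section 6.4 stratifies randomization by general disease type.

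Polypharmacy appears in section 2.1, which reports a systematic review of what geriatricians do for older adults with blood cancers: their interventions are described as "most often targeting nutrition, mood, physical function, polypharmacy, and social function". No analysis of non-cancer drugs alone is described anywhere.

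**The concern.** A geriatrician's review of polypharmacy would be expected to show mainly in non-cancer drugs. The number of cancer drugs depends largely on the disease and the treatment chosen, and it can change after baseline because entry is at the first consultation. Adding the two raises two separate issues.

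- **Precision.** Patient-to-patient variation in starting cancer treatment enters the outcome as noise.
- **Interpretation.** If co-management alters cancer treatment, the difference between arms in the total is the sum of that effect and any effect on non-cancer drugs. Opposite effects could cancel, and effects in the same direction could be mistaken for deprescribing.

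What is at stake is whether one secondary result can be interpreted. The survival endpoint is untouched.

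**Working it through.** The documents give no mean, standard deviation (SD), effect size or power for this outcome, so there is no stated figure to reproduce. What follows is an illustration.

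**Inputs from the documents:** 107 patients in usual care and 53 in co-management (section 6.3); significance level 0.05 (section 6.2, sidedness not stated; two-sided is assumed here).

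**Assumed inputs:** SD of the change in non-cancer drugs, 2 or 3; true effect of co-management, 1 or 1.5 fewer non-cancer drugs; a share p = 0.5 or 0.7 of patients start k = 1 to 4 cancer drugs by 3 months, equally in both arms and independently of the change in non-cancer drugs.

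**Step 1: variance.** Variance of total = SD² + k²·p·(1 − p).
- Smallest ratio (SD 3, p = 0.7, k = 1): (9 + 0.21)/9 = 1.02.
- Largest ratio (SD 2, p = 0.5, k = 4): (4 + 16 × 0.25)/4 = 2.0.

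These ratios ignore the disease-type adjustment, which would remove the part of the variation lying between diseases. A positive correlation between the two counts would raise them, and a negative one would lower them.

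**Step 2: standard error and bias with equal starts.** Standard error = SD × √(1/107 + 1/53) = SD × 0.168. Take SD 2, p = 0.7, k = 3.
- Non-cancer count: 2 × 0.168 = 0.34.
- Total: √(4 + 9 × 0.21) = 2.43, and 2.43 × 0.168 = 0.41.

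In 20,000 simulated trials with a true effect of −1 drug, the mean difference between arms was −1.00 for both measures. Equal starts therefore cost precision and cause no bias.

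**Step 3: power.** Power = Φ(effect/standard error − 1.96). The last column is the range over p and k.

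| Effect | SD | Non-cancer count | Total |
|---|---|---|---|
| 1 | 2 | 84.5% | 55.8–82.7% |
| 1 | 3 | 51.0% | 37.9–50.1% |
| 1.5 | 3 | 84.5% | 69.7–83.7% |
| 1.5 | 2 | 99.4% | 88.4–99.2% |

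**Step 4: means within an arm.** With p = 0.7 and k = 3, starts add 0.7 × 3 = 2.1 drugs in each arm. With one non-cancer drug fewer, the co-management arm shows −1 + 2.1 = +1.1. The arms must be compared; change within an arm is uninformative about deprescribing.

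**Step 5: unequal starts.** If co-management shifts the share starting treatment by 10 to 20 percentage points, at 2 to 3 drugs each, the contrast moves by between 0.1 × 2 = 0.2 and 0.2 × 3 = 0.6 drugs. For example, an effect of −1 on non-cancer drugs with 0.6 more cancer drugs gives −0.4 for the total.

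**The case against.** The other side has a good case on several points.

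- **A reader might infer that cancer drugs swamp any reduction in polypharmacy.** The documents do not support that. They give no variances, they show only that treatment can start within 3 months, and supportive care only is a listed treatment category. In the illustration the loss runs from negligible to substantial, and disease-type adjustment trims it.
- **A reader might infer that the Aim 2 estimate is biased.** It is not. Randomization gives an unbiased comparison of the total, and if co-management changes cancer treatment, that change is properly part of its effect on the total. The difficulty is what the total means.
- **A reader might take polypharmacy reduction to be an aim of the trial.** Section 2.1 names it only as background. The Aim 2 hypothesis is that "co-management by an embedded geriatrician will improve overall survival at one year", and total medication burden is a legitimate outcome in its own right.
- **A reader might extend the point to Aim 1**, expecting robust patients given more cancer drugs to look worse. Section 6.1 names treatment choice, time in hospital and survival, and specifies no medication analysis.
- **Treatment assignment is recorded separately**, which helps interpretation. This stands only in part: it is recorded at 6 months and in categories, so it does not show how many drugs of each kind make up the 3-month change.
- **Replacing the outcome now would be a post hoc switch.** Section 5.1 says Aim 2 is closed to enrollment, and section 8.0 schedules its analysis for June 2018 to August 2019, before the September 2020 changes that the current text describes. This stands, and it limits the fix to an addition.

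**Conclusion.** The point holds as one of interpretability, with a secondary cost in precision. The only planned measure of medication change pools two components that co-management could affect differently, over a window in which cancer treatment can start. Section 6.2 itself tests whether co-management affects treatment assignment, so the plan does not rule out such an effect. Where one occurs, neither a null nor a positive result for the total can be attributed to non-cancer drugs. In the illustration the shift is 0.2 to 0.6 drugs, against assumed effects of 1 to 1.5.

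Where treatment starts are equal across arms, the contrast is unbiased and its variance rises about 1.02- to 2-fold before disease-type adjustment. All these sizes rest on assumed SDs, effects and treatment-start rates, and on independence of the two counts. The outcome is secondary and the study was not powered on it, so this is a worthwhile refinement and no more.

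**What to change.** In Table 3, keep the change in total medications and add two separately analysed components over the same window: change in non-cancer medications and change in cancer medications. State which component counts supportive drugs started alongside cancer treatment; otherwise the non-cancer count may itself reflect treatment starts. If the Aim 2 analysis is already complete, label both components as supplementary.

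Do not try to solve this by adjusting for cancer treatment started after randomization. Co-management may affect that treatment, so the adjustment could introduce bias into a randomized comparison.

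The cost is a few lines in Table 3 and additional secondary comparisons, to be read with that in mind. The definition already requires both counts, so no new variable is needed, although drugs may have to be reclassified once the rule for supportive drugs is written down.
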